## 5. Conclusion

Our point estimates using the DerSimonian and Laird random effects meta-analysis method for disease progression rates at 3 years follow-up in the ablation arm and drug arm are 5.6% and 26.4% respectively, which are consistent with the physicians' estimates of 5% and 25% for ablation and drug therapy in the new study. Therefore, the published literature and experience in AF disease progression support our estimates of disease progression rate at 3 years follow-up and fully support the study design of a randomized trial testing whether early ablation treatment delays or prevents disease progression from paroxysmal AF to persistent or permanent AF compared with drug therapy.

## Appendix D: Safety Provisions - Drug Regulations

Countries for which the Attest study is subjected to national drug regulations (EudraCT number: 2012-002338-35, if applicable) the following provisions are applicable in addition to Section 12 of the protocol.

Definitions:

### **Suspected Unexpected Adverse Reaction** (Directive 2001/20/EC and CT-3):

An suspected unexpected adverse reaction (SUAR) is an adverse reaction, the nature or severity of which is not consistent with the applicable product information (e.g. investigator's brochure for an unauthorised investigational product or summary of product characteristics for an authorized product).

A SUSAR is defined as an event meeting the definition of a suspicion of SUAR and Seriousness definition (medicines).

To determine if an Serious Adverse Reaction of an AAD is expected or unexpected, Biosense Webster will refer to a list of SmPc's (e.g. [www.medicines.org.uk](http://www.medicines.org.uk)).

ATC	Class*	Name	Control
C07AA05	II	Propranolol	Rate
C07AA07	III	Sotalol	Rate/Rhythm
C07AB02	II	Metoprolol	Rate
C07AB03	II	Atenolol	Rate
C07AB04	II	Acebutolol	Rate
C07AG02	II	Carvedilol	Rate
C07AB12	NA	Nebivolol	Rate
C07AB07	II	Bisoprolol	Rate
C08DB01	IV	Diltiazem	Rate
C08DA01	IV	Verapamil	Rate
C01AA05	V	Digoxine	Rate
C01BA01	Ia	Quinidine	Rhythm
C01BC04	Ic	Flecainide	Rhythm
C01BD01	III	Amiodarone	Rhythm
C01BD07	III	Dronedarone	Rhythm
C01BC03	Ic	Propafenone	Rhythm
C01BD04	III	Dofetilide	Rhythm
C01BG07	Ic	Cibenzoline	Rhythm

\* Vaughan Williams Classification of Anti-arrhythmic drugs

Investigator responsibilities:

AAD related SUSAR's shall be reported by the Investigator to Biosense Webster immediately but not later than 24 hours of awareness.

NOTE: Pharmacovigilance reporting of events coming forth from drugs which are authorized medicinal products, shall be reported to the marketing authorization holder, unless otherwise indicated by institutional policies, EC / EB (or equivalent) policies, and local regulations.

Biosense Webster responsibilities

*Drug related events*

Any SUSARs must be handled and reported by Biosense Webster to the appropriate authorities (e.g., competent authorities) as well to the ECs / EBs (or equivalent) according to the prevailing regulations per country.

Biosense Webster shall perform standard expedited reporting to participating CAs, ECs / EBs and Investigators, unless otherwise indicated by national regulations:

Event Type	Timelines
SUSAR fatal or life-threatening	7 days (after the sponsor was first aware of the reaction)  8 days (any relevant additional information shall be sent within 8 days of the report)
SUSAR (other)	15 days

Biosense Webster shall not report adverse reactions related to other drugs than AAD's ( non-IMP) received by the subject and without interaction with the AAD (IMP).

PCI	Percutaneous Coronary Intervention
PI	Principal Investigator
PP	Per Protocol
PV	Pulmonary Vein
PVI	Pulmonary Vein Isolation
QoL	Quality Of Life
RA	Right Atrium
RF	Radiofrequency
RSPV	Right Superior Pulmonary Vein
RV	Right Ventricle
SADE	Serious Adverse Device Effect
SAE	Serious Adverse Event
SAP	Statistical Analysis Plan
SOC	System Organ Class
SOP	Standard Operating Procedure
SR	Sinus Rhythm
TEE	Transesophageal Echocardiography

ABBREVIATION	DEFINITION OR DESCRIPTION
TIA	Transient Ischemic Attack
TLG	Table, Listing, Graph
TTE	Transthoracic Echocardiography
TTM	Transtelephonic Monitoring
UADE	Unanticipated Adverse Device Effect
WHO	World Health Organization
VAS	Visual Analogue Scale

1. SYNOPSIS

This Statistical Analysis Plan (SAP) describes the planned analysis and reporting for Biosense Webster ATTEST protocol “Atrial Fibrillation Progression Trial” dated 9-Apr-2013 Version 3.0.

This post-marketing trial is a prospective, multi-center, randomized, controlled, two-arm, open-label, clinical study to determine whether early radiofrequency (RF) ablation treatment, using the CARTO[®] 3, CARTO[®] XP or CARTO[®] RMT System, and THERMOCOOL[®] Catheter Family in subjects with Paroxysmal atrial fibrillation (PAF), delays progression of atrial fibrillation (AF) compared with drug therapy (either rate or rhythm control) using current AF management guidelines.

The planned analyses identified in this SAP may be included in clinical study reports (CSRs), regulatory submissions, or future manuscripts. Also, post-hoc exploratory analyses not necessarily identified in this SAP may be performed to further examine study data. Any post-hoc, or unplanned, exploratory analyses performed will be clearly identified as such in the final CSR.

The following documents were reviewed in preparation of this SAP:

- Clinical Research Protocol Number 144, Version 3.0 dated 9-Apr-2013
- Case report forms (CRFs), Version 2.1 dated 01-Jul-2013

The reader of this SAP is encouraged to also read the clinical protocol, and other identified documents, for details on the planned conduct of this study. Operational aspects related to collection and timing of planned clinical assessments are not repeated in this SAP unless relevant to the planned analyses.

2. STUDY OBJECTIVES AND ENDPOINTS

2.1 Study Objective

The objective of this study is to determine whether in subjects with Paroxysmal AF (PAF), early RF ablation treatment using the THERMOCOOL[®] Catheter Family in conjunction with the CARTO[®] 3, CARTO[®] XP or CARTO[®] RMT System delays progression of AF compared with drug therapy (either rate or rhythm control) using current AF management guidelines.

2.2 Efficacy, Safety and Health Economic Endpoints

2.2.1 Efficacy Endpoints

The primary efficacy endpoint is the time to persistent AF/AT (excluding isthmus-dependent atrial flutter) at 3 years. According to the protocol, persistent AF/AT is defined as AF/AT lasting longer than 7 consecutive days or requiring termination by cardioversion after 48 hours.

Secondary efficacy endpoints are:

- Rate and time to persistent AF/AT at 1 year and 2 years, rate of persistent AF/AT by number of ablations at 3 years
- Number of repeat ablations and new anti-arrhythmic drugs (AAD) per subject throughout 3 years follow-up

- Rhythm (% subjects in sinus rhythm (SR), % subjects with recurrent AF/AT) throughout 3 years follow-up
- Factors associated with AF disease progression
 - Gender
 - Age
 - Left atrium (LA) size
 - HATCH score (score based on the five components: Hypertension, Age 75 years or older, Previous transient ischemic attack or stroke, Chronic obstructive pulmonary disease, and Heart failure)
 - Blood pressure
 - NYHA functional classification of heart disease
 - Presence of diabetes
 - Presence of hyperlipidemia or dyslipidemia
 - Presence of renal insufficiency
 - Presence of dementia

In addition, an alternative definition of the primary and the first secondary endpoint will be investigated based on the consensus statement of the HRS (Heart Rhythm Society, 2017). According to the HRS consensus statement 2017, persistent AF/AT is defined as continuous AF/AT that is sustained beyond 7 days.

2.2.2 Safety Endpoints

The key safety endpoints are:

- Catheter-related complications (adverse events)
- Drug related Adverse events-Adverse Drug Reactions (ADR)

2.2.3 Health Economic and Quality of Life Endpoints

The health economic endpoints are:

- Health care utilization (number and length of hospitalizations and unscheduled cardiovascular-related visits)
- Quality of Life (QoL) at 3 months, 6 months, 1 year, 2 years, and 3 years by change from baseline in
 - EQ-5D Score
 - AFEQT Score (collected in a subset of countries)

3. STUDY METHODS

3.1 Overall Study Design and Plan

ATTEST is a post-marketing, prospective, multi-center, randomized, controlled, two-arm, open-label, clinical study. For subjects randomized to the ablation group (Test), physicians are to perform procedures per institutional Standards of Care and processes required by their institution. For subjects randomized to the AAD group (Control), physicians are to manage medication in accordance with published, current

AF Management and with the Standard of Care and procedures required by their institution.

All subjects will be followed through 3 years. A subject in the medication group may request a cross-over to receive ablation

3.2 Selection of Study Population

This is a post-marketing study in subjects with Paroxysmal AF (PAF). Key inclusion criteria identified in the protocol are:

- Subjects with recurrent paroxysmal AF for at least 2 years, with ≥ 2 episodes over the last 6 months
- HATCH Score of at least ≥ 1 and ≤ 4
- Eligible for catheter ablation and for anti-arrhythmic or rate control medications, after having failed at least one but no more than 2 prescribed drugs (either anti-arrhythmic or rate control drug)
- Age 60 years or older
- LA diameter ≤ 55 mm by Transthoracic Echocardiography (TTE)
- Left ventricle (LV) ejection fraction $\geq 50\%$ when in sinus rhythm or LV ejection fraction $\geq 35\%$ when in AF
- Subject signed the Informed Consent Form and is able and willing to comply with protocol requirements, including all baseline and follow-up testing.

For the complete list of in- and exclusion criteria see the CTP, Sect. 9.3 and 9.4.

3.3 Method of Treatment Assignment and Randomization

Subject randomization will be 1:1 between catheter ablation (Test) and AAD therapy (Control). The randomized block design, stratified by gender and site, will be used to ensure a gender balance by treatment group at each site. Adaptive randomization will also be executed to further ensure the allocation balance of treatment groups by gender at each site. Subjects will be randomized in the order of their enrollment.

3.4 Treatment Masking (Blinding)

This is an open-label study.

4. ANALYSES AND REPORTING

4.1 Interim Analyses

An interim examination of the primary endpoint data will be performed at regular time intervals during the course of the trial to determine whether the study will be stopped for effectiveness or futility. Interim analyses will only be presented for the ITT and Safety Population. At the first interim analysis, sample size adjustment will be considered as specified in section 5. In addition, statistical interim reporting will also involve a review of adverse events. The results of the interim analyses will be reviewed by the Global Safety Monitoring Committee (GSMC) of Biosense Webster.

The GSMC will review the accumulated data no earlier than 1 year following the

study start and then approximately every 6 months thereafter if enrollment was on target. Data for the primary effectiveness endpoint and adverse events will be reviewed. Extracted data files and analysis programs for each interim report will be archived in the study files. Further details on the planned interim analyses are given in section 10.4. Moreover, it is indicated in the table of contents (section 15) which subset of tables, listings and figures will also be produced for the interim analysis.

4.2 Final Analyses

All final planned analyses identified in the protocol and in this SAP will be performed only after all relevant study data have been processed and the database has been locked. In addition, no database may be locked, random code unblinded, or analyses completed until this SAP has been approved.

Key statistics and study results will be made available to Biosense Webster following database lock and prior to completion of the final CSR.

Any post-hoc exploratory analyses completed to support planned study analyses, which were not identified in this SAP, will be documented and reported in appendices to the CSR. Any results from these unplanned analyses (post-hoc) will also be clearly identified in the text of the CSR.

4.3 SOPs

The following Premier statistics SOPs are applicable for this study:

SOP Number	SOP Title
SOP-ST-45.01	Statistical Analysis Plan
SOP-ST-47.01	Planning Execution and Delivery of Statistical Analyses
SOP-ST-48.01	Unblinding a Study for Statistical Analysis
SOP-ST-46.01	Development and Validation of SAS Programs

5. CHANGES TO PLANNED ANALYSIS

5.1 Changes for the final analysis

As the study was terminated early, without having met primary effectiveness or futility criteria at the most recent interim analysis, it is not fully obvious which alpha level to use for the primary efficacy analysis. However as the number and time points of the interim analyses had not been fixed in advance, it was decided to spend all alpha remaining for the final analysis, in other words to spend what is left from the total alpha. Moreover, after further discussion, it has been decided to update the calculation of the primary endpoint to use procedure date as start date for time to event calculation rather than randomization date (see section 8.3).

It also was decided to delete some of the analyses originally planned in the protocol:

- For secondary endpoint “factors associated with AF disease progression”, only the main analyses will be performed, and some of the supporting models were deleted
- Analysis of site heterogeneity will not be performed

Moreover, a sensitivity analysis for the primary endpoint and first secondary endpoint was added, using an alternative definition for the primary endpoint based on the consensus statement of the HRS (Heart Rhythm Society, 2017).

5.2 Changes for the interim analyses

Before the first interim analysis, some updates had been made to the originally planned method for re-calculation of operating characteristics. Section 10.4 reflects those updates.

6. SAMPLE SIZE DETERMINATION

A total sample size of 322 (161:161) subjects will be required to ensure 85% power to detect the effect size measured by negative log of the hazard ratio equal to 1.1541 (treatment group over control group).

$$-\log_e \left(\frac{\hat{\lambda}_t}{\hat{\lambda}_c} \right) = -\log_e \left(\left(-\frac{\log_e(0.95)}{3} \right) / \left(-\frac{\log_e(0.85)}{3} \right) \right) = 1.1541$$

This calculation assumes a 50% cross-over rate from the AAD group to the ablation group, a 10% drop-out rate in each group over the 3 year follow-up period, and 1.5 years accrual time. This calculation is based upon one-sided superiority testing with alpha equal to 0.025. Using meta-analysis, the rates of disease progression at the end of follow-up are estimated to be 25% and 5% in the AAD and ablation group, respectively (see the point estimate justification document for details, Appendix C of the CTP). The cross-over to ablation is reflected in the use of the proportion 0.85 instead of 0.75 in the formula above. The sample size calculation is based upon the method developed by Rubinstein, Gail and Santner⁴ (RGS, 1981) and also incorporates group sequential design with multiple interim looks.

Adaptive Sample Size Re-estimation

Due to the uncertainties associated with the cross-over rate and the effect size, the sample size will be reestimated at the time of the first interim analysis. Conditional power (CP) will be calculated at that time to determine how promising the interim results are. CP is defined as the conditional probability that the final result will exceed a critical value given the data observed thus far, and the assumption that the trend to be observed in the remainder of the study⁵ will follow the expectation, which was used in the original sample size calculation. If the CP is less than 0.3, then the study is considered not promising, and the sample size will not be increased. If the CP is

greater than 0.9, then the study is deemed fully powered and the sample size will not be increased. If the CP falls in the promising zone (0.3-0.9), the sample size will be re-estimated based upon the observed effect size.

In detail, the following formula will be applied to re-estimate the sample size:

$$M = N \left(\frac{\delta}{\Delta} \right)^2$$

where M is the updated sample size per group, N is the initially planned sample size per group, δ is the expected effect size (1.1541) and Δ is the effect size observed at the time of interim analysis:

$$\Delta = -\log_e \left(\frac{D_t/T_t}{D_c/T_c} \right)$$

where D_t and D_c are the number of deaths observed in the treatment and control group and T_t / T_c are the total times observed (up to the time of censoring) in the respective groups.

In case the re-estimated sample size is unrealistic high, the sponsor will select one of the following 3 options:

- Determine the maximum realistic sample size and continue the study to enroll the maximum number of patients
- Continue study as planned to enroll original planned sample size
- Stop the study for futility.

In case the sample size will be increased, the CHW (Cui, Hung and Wang) adaptive method will be used for statistical testing.⁶

The CHW weighting will be applied according to the following formula:

$$Z = \sqrt{t_{adj}} Z_{0;adj} + \sqrt{(1 - t_{adj})} Z_{adj;max}$$

Where Z is the final test statistic, t_{adj} is the (planned) information fraction at the time of sample size adjustment, $Z_{0;adj}$ is the test statistic derived from the data available at the time of sample size adjustment, and $Z_{adj;max}$ is the test statistic derived from data collected after the time of sample size adjustment, including a possibly increased sample.

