#### Adaptive Sample Size Re-estimation:

Due to the uncertainties associated with the cross-over rate and the effect size, the sample size will be reestimated 1.5 years after the start of enrollment or at the end of the enrollment

---

$$^f -\log_e \left( \frac{\hat{\lambda}_t}{\hat{\lambda}_c} \right) = -\log_e \left( \left( -\frac{\log_e(0.95)}{3} \right) / \left( -\frac{\log_e(0.85)}{3} \right) \right) = 1.154$$

whichever occurs earlier. Conditional power (CP) will be calculated at that time to determine how promising the interim results are. CP is defined as the conditional probability that the final result will exceed a critical value given the data observed thus far, and an assumption about the trend to be observed in the remainder of the study. If the CP is less than 0.3, then the study is considered not promising and the sample size will not be increased. If the CP is greater than 0.9, then the study is deemed fully powered and the sample size will not be increased. If the CP falls in the promising zone (0.3-0.9), the sample size will be reestimated based upon the observed effect size and the CHW (Cui, Hung and Wang). Adaptive Method will be used for statistical testing.

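### SAP 6 sample-size re-estimation ignores the direction of the observed effect: a trend against ablation can count as promising and give the same increase as the mirror-image benefit

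*SAP*

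**What the plan says.** The design in SAP 6: "A total sample size of 322 (161:161) subjects will be required to ensure 85% power to detect the effect size", with the "negative log of the hazard ratio equal to 1.1541 (treatment group over control group").

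Re-estimation in SAP 6 has two stages.

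- **Gate.** CP assumes that the trend in the rest of the study "will follow the expectation, which was used in the original sample size calculation". SAP 10.4 likewise uses the expected effect for CP. Below 0.3 or above 0.9 the sample is not increased; between them it is re-estimated from the observed effect.
- **Size.** M = N(δ/Δ)², "where M is the updated sample size per group, N is the initially planned sample size per group". δ is 1.1541 and Δ = −ln[(D_t/T_t)/(D_c/T_c)], from event counts (which the SAP calls deaths) and total observed times.

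There is no condition on the sign of Δ, no rule for an arm without events and no stated floor. If M is unrealistically high, the sponsor chooses among a realistic maximum, the original size, or stopping for futility. No maximum is given in advance. If the sample is increased, the CHW-weighted statistic replaces the ordinary one (SAP 6 and 10.4). SAP 10.1, the primary analysis, names only a log-rank test.

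On timing, Protocol 13.4 says "the sample size will be reestimated 1.5 years after the start of enrollment or at the end of the enrollment", whichever is earlier. SAP 6 says "the sample size will be reestimated at the time of the first interim analysis", and SAP 4.1 agrees. SAP 5.2, on changes for the interim analyses, mentions only how operating characteristics are recalculated.

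**The concern.** Re-estimation exists to rescue a study that is promising but underpowered. Here the two stages use different effects. The gate uses the planned effect, which a handful of events can barely move; the size uses the observed effect with its direction squared away. A modest trend against ablation can therefore pass the gate and lead to a larger trial. Because SAP 10.4 stops for futility only when CP is below 0.3, the same trend also escapes that rule.

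The consequence still open is the primary test. Whether the sample was increased decides whether the final statistic is weighted, and the current SAP does not say. SAP 15.1 marks the re-estimation table as not required for the final analysis, so the final output would not show it either.

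**Working it through.** **Inputs.** N = 161 per group, δ = 1.1541, one-sided alpha 0.025, power 85% (SAP 6). Final look at 28 events with bound 2.0507; illustrative first look at 5 events, 12 months (SAP 10.4 table). First look at about 25% of events, so 0.25 × 28 = 7 (Protocol 13.9.2). Assumptions: equal person-time per arm; Z ≈ (D_c − D_t)/√D; information fraction t = D/28.

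**The plan's own figures.** −ln[ln(0.95)/ln(0.85)] = 1.1532, against 1.1541 printed; the difference is immaterial. Drift at 28 events is θ = 1.1541 × √(28/4) = 3.053. Power is Φ(3.053 − 2.0507) = 0.84 at the final bound and Φ(3.053 − 1.96) = 0.86 at the nominal value. The stated 85% lies between, so 28 events and θ = 3.053 are a fair basis.

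**Formulas.** CP = Φ{[Z√t + θ(1 − t) − 2.0507]/√(1 − t)}. With equal person-time, Δ = −ln(D_t/D_c) and M = 161 × (1.1541/Δ)².

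**Two cases in full.**

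- 3:2 at 5 events (Test:Control): Z = −1/√5 = −0.447 and t = 0.179. CP = Φ[(−0.189 + 2.508 − 2.0507)/0.906] = Φ(0.296) = 0.62. M = 161 × (1.1541/0.4055)² = 1304.
- 5:2 at 7 events: Z = −3/√7 = −1.134 and t = 0.25. CP = Φ[(−0.567 + 2.290 − 2.0507)/0.866] = Φ(−0.378) = 0.35. M = 161 × (1.1541/0.9163)² = 255.

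| Events | Test:Control | CP | Δ | M per group by formula |
|---|---|---|---|---|
| 5 | 0:5 | 0.94 | undefined | gate closed |
| 5 | 1:4 | 0.87 | +1.386 | 112 |
| 5 | 2:3 | 0.76 | +0.405 | 1304 |
| 5 | 3:2 | 0.62 | −0.405 | 1304 |
| 5 | 4:1 | 0.45 | −1.386 | 112 |
| 5 | 5:0 | 0.295 | undefined | borderline |
| 7 | 2:5 | 0.82 | +0.916 | 255 |
| 7 | 5:2 | 0.35 | −0.916 | 255 |

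**Sensitivity.** With t = 0.22 (the table's fraction) in place of 5/28, or 1.96 in place of 2.0507, CP ranges over 0.55–0.65 for 3:2, 0.36–0.49 for 4:1 and 0.20–0.33 for 5:0. At 9 events, 5:4 against ablation still gives CP 0.42.

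**How often.** Under the planned effect the Test share of events is e^(−1.1541)/(1 + e^(−1.1541)) = 0.24. At 5 events, 1:4 is the likeliest split: 5 × 0.24 × 0.76⁴ = 40%. The splits 3:2 and 4:1 together have about 9%. If the true hazard ratio is 1, they have (10 + 5)/32 = 47%.

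**Zero events.** Δ then needs the log of zero or a division by zero, so M is undefined. At 5 events the gate excludes 0:5 and nearly excludes 5:0. With no control events and only 2, 3 or 4 events in all, CP is 0.66, 0.55 and 0.42, inside the zone when t = D/28. With t = 0.22 only the 2-event case stays in, at 0.35.

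**The case against.** The strongest reply is that the step is over. The study ended early after interim analyses (SAP 5.1), and the rule can no longer resize it. Whether CHW applies turns on a fact, whether the sample was increased, and not on the quality of the formula. This stands as a limit on the point, but that fact is not recorded.

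Four stronger readings are tempting, and the documents do not support them.

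- **That the rule could shrink the trial, even to nothing.** Protocol 13.3 and SAP 6 speak only of increasing or not increasing, so M = 112 reads as no increase. With an empty arm M is undefined rather than zero, and at 5 events the gate largely keeps that case out.
- **That it could multiply the trial eight-fold on noise.** M = 1304 is eight times 161, but SAP 6 sends an unrealistically high M to three sponsor options, including keeping the original size or stopping. At 5 events neither split against ablation compels an increase: 4:1 gives 112 and 3:2 goes to those options. The 5:2 split at 7 events differs, because 255 per group need not strike anyone as unrealistic.
- **That this trial was mis-sized.** SAP 10.4 calls its table an example and fixes no look times. SAP 4.1 says only that the first review comes no earlier than one year. Neither the event count nor the date of the actual first look is given, so it cannot be shown that the step came before 1.5 years.
- **That CP must follow the current trend.** CP under the design effect is a defined and legitimate choice. With current-trend CP, 2:3 falls to 0.14, while 1:4 gives 0.89 with M below 161, so no 5-event split would lead to an increase.

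**Conclusion.** The concern holds as a defect in the written rule and a gap in the record. The rule lacks a sign condition, a floor, a zero-event provision and a stated maximum, and its gate admits trends against ablation. The clearest case is 5:2 at 7 events: CP 0.35 and 255 − 161 = 94 more subjects per group, the same M as for 2:5. That split is uncommon: 21/128 = 16% of 7-event outcomes at hazard ratio 1, and about 1% under the planned effect. Under the planned effect the likeliest 5-event split (1:4) gives M below N, which the increase-only wording implies means no increase.

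These figures assume equal person-time, t = events/28, the approximate Z, and 5 or 7 events at the first look. What remains open for the final analysis is which statistic SAP 10.1 will use, and why the protocol and SAP give different times for the step.

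**What to change.** In SAP 6, state that the sample is increased only if Δ > 0 and both arms have events, with M = max(161, min(prestated maximum, N(δ/Δ)²)). Reconcile the timing in SAP 4.1 and 6 with Protocol 13.4, and correct the reference in SAP 4.1, which points to section 5 for a rule that is in section 6.

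Because the step is complete, the rule should not be rewritten as though it had governed the decision. Record in SAP 5.2 the CP, Δ and M obtained, the date and number of events, and whether the sample was increased. Then state in SAP 10.1 whether the final test is the plain log-rank or the CHW-weighted statistic.

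A current-trend CP for the gate is optional; the sign condition and floor do the necessary work without it. The cost is a few sentences of SAP text. The downside of the tighter rule is fewer opportunities to increase the sample.
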